#### 6.8.7. Growth Velocity (cm/year)

Ulna length measurements is used for indirect measure of annualized growth velocity (cm/year) for subjects under the age of 18. For subjects that enter the study at age 18 or turn 18 during the study, the last recorded ulna length/height will be used for the remainder of the study.

Annualized growth velocity (cm/year) is defined to be the ratio of change in height (cm) between the baseline and post-baseline to the duration of the observed time (years), where height is estimated by the formula described in [Section 6.3.1](#).

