6.2.1. Vital Signs (including Weight)

Vital signs to be collected include; heart rate, blood pressure, respirations and temperature:

- Heart rate should be collected as beats/min
- Respiration rate should be collected as breaths per minute
- Systolic and diastolic blood pressure should be collected from subjects in seated position (mmHg)
- Temperature should be taken using any standard method and captured as °F or °C

Weight is collected during screening, and every 12 weeks (or within 14 days prior) after Day 0. Height is collected as ulna length measurement by respiratory technician only, during PFT visits. For subjects that enter the study at age 18 or turn 18 during the study, the last recorded ulna length/height will be used for the remainder of the study.

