### **4.3. Safety Assessments**

- All treatment emergent adverse events (TEAEs), treatment emergent serious adverse events (TESAEs), clinically significant laboratory test abnormalities, discontinuation of treatment due to treatment-related AEs, hypersensitivity/anaphylactic reactions, and infusion reactions
- Number and percentage of subjects with hospitalizations due to any serious adverse events with pulmonary and/or cardiac cause(s)
- Number and percentage of subjects with bone fractures
- Ulna length measurements for indirect measure of growth velocity (cm/year) for subjects under the age of 18

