### **6.3.1. Demographics and Baseline Characteristics**

Demographic parameters and other important baseline and disease characteristics will be summarized by treatment group. These include but may not be limited to age, age group ( $\leq 16$

years, >16 years), ethnicity, race, weight, body-mass index (BMI), side of dominant hand, and body surface area (BSA), PUL 2.0 total score and subscores.

Computation formula:

$$BSA = [\text{Weight}^{0.425} (\text{kg}) * \text{Height}^{0.725} (\text{cm})] \times 0.007184$$

$$\text{Age} = \text{Year of informed consent date} - \text{Year of birth}$$

Height (cm) = 4.605 \* Ulna length (cm) + 1.308 \* Age at PFT assessment + 28.003, where age < 18 years old during PFT visits; For subjects that enter the study at age 18 or turn 18 during the study, the last recorded ulna length/height will be used for the remainder of the study.

Descriptive statistics (n, mean, standard deviation, median, interquartile (Q1, Q3), range (=minimum, maximum)) will be presented for continuous variables. Frequency distributions (number and percentage of subjects) will be presented for categorical variables.

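### SAP 6.8.7 carries height forward after age 18 without saying that observed time stops, so on its most natural reading growth velocity is understated for boys who turn 18 on study

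*SAP*

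**What the plan says.** Growth velocity is a declared safety assessment in both documents. SAP 4.3 lists it as "Ulna length measurements for indirect measure of growth velocity (cm/year) for subjects under the age of 18", and Protocol 8.3.7 names it among the safety analyses without a calculation rule.

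The derivation is in SAP 6.8.7, in three steps:

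- Population: "Ulna length measurements is used for indirect measure of annualized growth velocity (cm/year) for subjects under the age of 18". The section does not say whether age is judged at baseline or at each assessment.
- Carry-forward: for subjects who enter at 18 or who "turn 18 during the study, the last recorded ulna length/height will be used for the remainder of the study".
- Calculation: velocity is "the ratio of change in height (cm) between the baseline and post-baseline", relative "to the duration of the observed time (years), where height is estimated by the formula described in" SAP 6.3.1. No post-baseline visit is named, and no end date is given for observed time.

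The height formula in SAP 6.3.1 carries its own age limit: "Age at PFT assessment + 28.003, where age < 18 years old during PFT visits". The carry-forward rule also stands beside that formula. In Protocol 6.2.1, where height is an ulna measurement taken at lung function visits, the rule is that "the last recorded ulna length/height will be used for the remainder of the study". The protocol does not link this rule to growth velocity.

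**The concern.** A carried-forward height is harmless when it feeds a percent-predicted spirometry value. In a growth rate it turns a missing measurement into zero growth. If the numerator stops at the last real measurement and the denominator runs on to the visit, velocity falls for every boy who turns 18 on study. It is exactly zero for one who turns 18 before his first post-baseline measurement. This does not depend on the height formula; any formula would show it.

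The measure is there to detect a growth effect in steroid-treated boys, and Protocol 2.2 itself notes short stature in this disease. Artificial low values pull both arm means down. In a trial of this size, a chance imbalance in 17-year-olds could then add to, or hide, a difference in growth.

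**Working it through.** The documents give no figure for growth velocity, so there is nothing to reproduce. The check compares the derivations that the wording allows.

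**Inputs from the documents**
- Height (cm) = 4.605 × ulna + 1.308 × age + 28.003 (SAP 6.3.1).
- Post-baseline measurement at Weeks 12, 22, 32, 42 and 52 (SAP Appendix 2, Table 8; ulna is measured at lung function visits, Protocol 6.2.1).

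**Assumptions (not in the documents)**
- Constant ulna growth, illustrated at 0.5 cm/year.
- 18th birthdays spread evenly over the 52 weeks.
- 8%, 1/6 or 25% of under-18 boys turn 18 on study. The 1/6 corresponds to ages spread evenly over 12 to 17.
- Equal true velocity at all ages.

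**Step 1: true velocity.** 4.605 × 0.5 + 1.308 = 3.61 cm/year. For ulna growth of 0 and 1.0 cm/year it is 1.31 and 5.91.

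**Step 2: Week 52 velocity for a boy last measured before 18 at Week w.**
- Reading (a): height frozen, time runs to Week 52. Velocity = true value × w/52.
- Reading (b): height frozen, time ends at Week w. Velocity = true value.
- Reading (c): only ulna frozen, the age term continues. Velocity = 4.605 × 0.5 × w/52 + 1.308.

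| Last measured before 18 | w/52 | (a) cm/year | (b) cm/year | (c) cm/year |
|---|---|---|---|---|
| Baseline only | 0% | 0 | missing | 1.31 |
| Week 12 | 23% | 0.83 | 3.61 | 1.84 |
| Week 22 | 42% | 1.53 | 3.61 | 2.28 |
| Week 32 | 62% | 2.22 | 3.61 | 2.72 |
| Week 42 | 81% | 2.92 | 3.61 | 3.17 |

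The percentages under (a) do not depend on the assumed growth rate.

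**Step 3: average under (a).** A birthday before Week 12 has probability 12/52 = 0.231 and gives zero. Each of the four later intervals has probability 10/52. Mean share retained = (10/52) × (12 + 22 + 32 + 42)/52 = 0.399.

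**Step 4: arm mean at Week 52 under (a).** Understatement = s × (1 − 0.399), where s is the share turning 18:
- s = 0.08: 4.8%
- s = 1/6: 10.0%
- s = 0.25: 15.0%

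**Step 5: where it is smaller.** At Week 12 with s = 1/6, only boys who turn 18 before that visit are affected: 1/6 × 12/52 = 3.8%. If the oldest boys grow at half the rate of the others (assumption), the Week 52 figure for s = 1/6 is (1/6 × 0.5 × 0.601)/(5/6 + 1/6 × 0.5) = 5.5%.

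**Which reading the text favours.** The carry-forward rule already stands in SAP 6.3.1 for height in general. Repeating it in a section that derives only growth velocity has a purpose only if carried-forward heights enter that velocity. If records from age 18 on were simply dropped, no later height would be needed there. The sentence also covers boys who enter at 18, who are outside the endpoint population. That suggests a height convention moved into this section without being adapted to growth.

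**The case against.** The strongest reply is that the running denominator is an inference. The SAP divides by observed time, and a carried-forward height is not an observation, so the time can be read as ending at the last real measurement. That is reading (b), which has no bias under constant growth. Likewise, if under 18 is judged at each assessment, as the age limit on the height formula suggests, records from 18 onward drop out and the bias goes with them. Both replies stand. A reader might infer that the SAP certainly gives these boys a false or zero velocity; the text does not go that far. Nor is height frozen at the 18th birthday: it is held at the last recorded measurement.

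The consequence is also limited. Growth velocity has no model or hypothesis test and is outside the testing sequence in SAP Table 1. A reader might infer a biased treatment comparison, but the rule is the same in both arms of a randomised, blinded trial. It creates no systematic difference when true growth is equal. A chance imbalance in 17-year-olds would also move a raw mean after the fix, wherever growth varies with age.

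Few boys are involved. SAP Section 7 reports 97 dosed. If all were under 18 and 1/6 turned 18 on study, that is about 16 boys across both arms, with about 4 at zero (16 × 0.231). With no upper age limit in Protocol 4.1, the number may be lower.

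What remains is that nothing in 6.8.7 excludes reading (a), and the wording favours it. The same boy can get different velocities depending on the programmer.

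**Conclusion.** The point holds in conditional form. SAP 6.8.7 places an explicit carry-forward rule inside an under-18 growth measure and does not end observed time at the last real measurement. On the most natural reading, a boy who turns 18 on study keeps on average about 40% of his true Week 52 velocity, and about 23% of such boys get zero. The Week 52 arm mean is then about 5% to 15% too low.

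That range rests on reading (a), evenly spread birthdays, 8% to 25% turning 18 on study, and equal growth at all ages. It is smaller at earlier visits or if the oldest boys grow more slowly. The age mix is not in the documents. The primary and secondary efficacy results are untouched. The case for acting is that the rule can give wrong values in a declared safety measure and is cheap to repair.

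**What to change.** In SAP 6.8.7:

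- Limit the carry-forward sentence to the height used for percent-predicted spirometry.
- Compute velocity only from ulna measurements taken before the 18th birthday: the change in height from baseline to the last such measurement, divided by the time between those two dates.
- Set velocity to missing when there is no post-baseline measurement before 18.
- State a minimum interval for annualising, or flag values from short intervals.

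The birthday test should use age at each lung function visit, which the height formula already needs. The age formula in SAP 6.3.1 subtracts calendar years only, as of consent.

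The cost is a few sentences of SAP text and a small derivation change. There are two downsides. A few boys who turn 18 before Week 12 leave the table. Velocities annualised over short intervals are also noisy: an assumed 1 mm ulna error over 12 weeks becomes 0.1 × 4.605 × 52/12 = 2.0 cm/year. That is why the minimum interval or flag is needed.

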#### **6.8.8. Bone Fractures**

Bone fractures are summarized, but not limited to, by types of bone fractures, namely, long bone fractures and vertebral compression fractures.

- Long bones fractures
  - Lower extremities: femur (thigh); tibia; fibula (leg), metatarsus, phalanges (foot). Joint fractures: hip, knee, ankle;
  - Upper extremities: humerus (arm); radius; ulna (forearm); metacarpus, phalanges (hand, palm); Joint fractures: shoulder, elbow, wrist.
- Vertebral compression fractures

Spine compression fracture, vertebral compression fracture, spine fracture, or vertebral fracture indicate the same type of vertebral compression fractures. The level of compression fracture is indicated by vertebrae: C1–C7 (cervical spine); T1–T12 (thoracic spine); L1–L5 (lumbar spine); S1–S5 (sacrum, fused), coccyx (3-5, fused).
- Other

Hip bone fracture; foot fracture (other than long bones); hand fracture (other than long bones); other.

#### **6.8.9. Subgroup Analyses of Safety Endpoints**

The subgroup analysis will be conducted to safety endpoints such as TEAE and TESAE. The subgroups are specified in [Section 6.6.4](#), not including subgroup defined by Baseline PUL level.

### **6.9. Biomarker Endpoint Analysis**

A sample for Tryptase at time of immunogenic reaction will be collected. A listing will be provided for the data.

### **6.10. Immunogenicity Analysis**

A listing will include all available Human Anti-Human Antibody (HAHA, ADA) samples will be provided. ADA analysis will be conducted in the OLE phase of the study.

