
Sample Size Calculations:
 
This study is planned to enroll approximately 92 subjects with a 1:1 randomization ratio of assigning to pamrevlumab and placebo, respectively. With PUL version 2.0, the sample size of approximately 92 subjects is needed to detect a treatment difference of 2.0 between treatment arms in change from baseline in the total score of PUL at Week 52, assuming a standard deviation of 2.9 with a 90% power, based on a two-sided two-sample t-test at the alpha level of 0.05.
 
Statistical Analysis Methods:
 
The primary endpoint, change in the total score of Performance of Upper Limb [(PUL) 2.0 version], from baseline to Week 52 will be analyzed using a random coefficient model (RCM) with treatment, visit, visit-by-treatment interaction, and baseline total score of Performance of Upper Limb value as fixed effects; the intercept and linear slope of visit as random effects. The primary analysis will be based on observed data from subjects in the Intent to Treat (ITT) population.
 
As sensitivity analysis, the analysis of covariance model (ANCOVA) with Multiple Imputations (ANCOVA –MI) will be also applied. The model will include treatment and baseline total score of PUL value. The primary analysis will be based on the ITT population.
 
The change from baseline to Week 52 in ppFVC will be analyzed using a random coefficient model with treatment, visit, visit-by-treatment interaction, and baseline ppFVC as fixed effects; the intercept and linear slope of visit as random effects. The analysis will be based on observed data from subjects in the ITT population.
 
The change from baseline to Week 52 ppPEF will be analyzed using a random coefficient model with treatment, visit, visit-by-treatment interaction, and baseline ppPEF as fixed effects; the intercept and linear slope of visit as random effects. The analysis will be based on observed data from subjects in the ITT population.
 
For other secondary endpoints, ANCOVA model will be used in continuous variables; logistic regression model in binary variables; Cox regression model in time-to-event variables. The analysis models will include appropriate baseline factors. Impact of missing data will be evaluated based on various assumptions.
 
Safety Analyses:
 
All treatment-emergent adverse events (TEAEs) will be summarized by treatment arm, including: TEAEs Grade ≥ 3, treatment-emergent serious adverse events (TESAEs), deaths, and TEAEs leading to study or treatment discontinuation.
 
Clinically significant changes from baseline in vital signs, laboratory tests will be summarized by treatment arm. Additionally, hypersensitivity/anaphylactic reactions will be monitored and the impact of immunogenicity will be assessed, during the entire course of the trial.

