6.2.3.2.2. Human Anti-Human Antibodies (HAHA)

Plasma samples will be collected for evaluation of human anti-human antibodies (HAHA), specific to the impact of neutralizing anti-drug antibodies (HAHA-NA) and the impact on immunogenicity, in all subjects according to the SOAs in [Appendix 1](#) and [Appendix 2](#). A specialty laboratory will measure HAHA titers using a validated assay.

Samples/subjects with positive/specific HAHA results will be subject to evaluation of neutralizing antibody (HAHA-NA) assays and analyses. The prevalence and duration of binding and neutralizing antibodies and the effect of these antibodies on the pharmacokinetics, pharmacodynamics markers, efficacy, and safety of pamrevlumab will be assessed.

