APPENDIX 3. OPEN LABEL EXTENSION (OLE)

This is an optional open-label, single arm extension to evaluate long-term efficacy and safety of pamrevlumab in DMD subjects. Subjects who complete week 52 of the main study (regardless of the number of study drug infusions received) will be eligible to participate in the open-label extension (OLE) where all subjects will be treated with pamrevlumab. After completing Week 52 of the main study, participants in the OLE will then move to Week 2 of the OLE. The EOS visit will be completed at the end of participation in the OLE. If a subject discontinues the main study early for any reason, they will not be eligible for inclusion in the OLE.

Each subject will receive pamrevlumab (35 mg/kg) intravenously, every 2 weeks until the last subject from the phase 3, DMD program completes 52 weeks of treatment on OLE or when Pamrevlumab is commercially available or when the Sponsor decides to end the study.

Upon completion of the trial, subjects will be asked to return to the investigative site 4 weeks after their last treatment visit to complete a final follow-up visit and will receive a final safety follow-up phone call 60 days (+3 days) after the last dose. See parent study protocol for detailed information on study drug formulation, storage, and administration. All subjects will receive pamrevlumab in an open-label manner. Note: No unblinding of subject's treatment assignment in the main study will occur for purposes of OLE participation.

The following conditions are excluded for continued participation in this OLE phase:

- Use of any investigational drugs, or participation in a clinical trial with an investigational new drug, other than participation in the main study.
- History of allergic or anaphylactic reaction to human, humanized, chimeric or murine monoclonal antibodies, or experienced an allergic or anaphylactic reaction to study drug or any component of study drug.
- Subjects who withdrew informed consent while participating in the main study, or who discontinued early from the main study for any reason.
- The Investigator judges that the subject is not suitable for participation, or is unable to fully participate in the OLE phase and complete it for any reason, including inability to comply with study procedures and treatment, or any other relevant medical or psychiatric conditions

Endpoints

Function assessment:

- Annual mean change in the total score of Performance of Upper Limb [(PUL) 2.0 version].

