## 1. INTRODUCTION

This statistical analysis plan (SAP) provides a more technical and detailed elaboration of the statistical analyses of study data as specified in the Study Protocol FGCL-3019-093 Amendment 6, 01 November 2022. Specifications of tables, figures, and listings (TFL) are contained in a separate document. The statistical analyses and summary tabulations described in this SAP will provide the basis for the results sections of the clinical study report (CSR) for this study. The SAP will be finalized and signed off prior to database lock (DBL). Any major modification of this SAP after the signoff will be documented in an SAP amendment or the CSR.

This SAP is only for the main study period. The Open Label Extension (OLE) will have a separate SAP. A population PK analysis, as well as an exposure-response analysis, will be defined in a separate PK analysis plan.

Based on regional regulatory filing needs, regional specific population will be analyzed following this same SAP. Refer to [Appendix 6](#) if regulatory submission in China is pursued.

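### SAP 6.10 provides only a listing of the main-study anti-drug antibody data and defers the analysis to the open-label extension, which falls short of the protocol's commitment and is not recorded as a change

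*SAP*

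**What the plan says.** SAP 6.10 has two sentences. The first plans a listing: "A listing will include all available Human Anti-Human Antibody (HAHA, ADA) samples will be provided". The second places the analysis elsewhere: "ADA analysis will be conducted in the OLE phase of the study". SAP Section 1 limits this SAP to the main study and adds that "The Open Label Extension (OLE) will have a separate SAP". That document was not supplied.

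Protocol 6.2.3.2.2 sets a wider task. It names "The prevalence and duration of binding and neutralizing antibodies and the effect of these antibodies on the pharmacokinetics, pharmacodynamics markers, efficacy, and safety" of pamrevlumab as things that will be assessed. The Safety Analyses paragraph of the protocol synopsis adds that "the impact of immunogenicity will be assessed, during the entire course of the trial".

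Protocol Appendix 2 schedules HAHA and HAHA-NA draws for all subjects at Day 0, Weeks 24, 32, 40 and 48, and Week 56/EOS or ET, with a further draw at any immunogenic reaction. Neutralizing assays are run only where HAHA is positive.

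Protocol Appendix 3 describes the extension as optional and single arm. It bars subjects who "experienced an allergic or anaphylactic reaction to study drug or any component of study drug", and subjects who withdrew consent "or who discontinued early from the main study for any reason".

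**The concern.** Pamrevlumab is a monoclonal antibody given every two weeks for a year. How often antibodies form, and whether they go with lower concentrations or with reactions, are ordinary safety questions for its main-study report. The protocol says they will be answered, and Protocol 8.4 leaves the detailed methods to the SAP. The SAP supplies none for the main study.

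The main study is the only part with a placebo arm. That arm shows how often the assay reads positive without exposure to drug. The extension has no concurrent equivalent. A subject-level listing leaves readers to build their own incidence table, with no prespecified definition of baseline-positive, treatment-emergent or persistent.

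**Working it through.** **1. Commitment against plan**

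| Item | Protocol | Main-study SAP |
|---|---|---|
| Prevalence of binding antibodies | To be assessed (6.2.3.2.2) | Listing only (6.10) |
| Duration | To be assessed (6.2.3.2.2) | None |
| Neutralizing antibodies | To be assessed (6.2.3.2.2) | No summary |
| Effect on PK | To be assessed (6.2.3.2.2) | 6.7 summarizes concentrations by visit, not by ADA status |
| Effect on safety | To be assessed (6.2.3.2.2, synopsis) | 6.8.6 summarizes hypersensitivity, infusion and anaphylactic reactions, not by ADA status |
| Effect on efficacy | To be assessed (6.2.3.2.2) | None |
| Recorded as a change | n/a | Not in Section 7 |

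Section 7 does record smaller changes, such as the move from MMRM to ANCOVA for the MRI endpoints. Population PK and exposure-response sit in a separate plan (Protocol 8.3.6, SAP 1). Neither document says that plan includes ADA status.

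**2. How much data is affected**

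A subject who does not roll over has six scheduled HAHA timepoints. Appendix 1 footnote p limits the Week 56 visit to subjects not entering the extension, and Appendix 3 moves the EOS visit to the end of the extension. A subject who rolls over therefore has five.

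Subject numbers are 92 planned (Protocol 8.1) and 97 dosed (SAP 7). At full attendance:
- all roll over: 5 × 92 = 460 to 5 × 97 = 485 samples;
- none roll over: 6 × 92 = 552 to 6 × 97 = 582 samples.

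The range is about 460 to 580, before missed visits and any extra draws at reactions.

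**3. What a main-study table could show**

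Protocol 3.4.1 gives about 46 subjects per arm. With no positives among 46, the upper two-sided 95% Clopper-Pearson limit is 1 − 0.025^(1/46) = 7.7%. That is imprecise but informative, and the placebo arm gives the same statistic for background positivity.

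**4. What an analysis of extension entrants alone could do (conditional)**

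The documents give no ADA rate and no rate of extension entry, so every input here is assumed. Let p be the true ADA-positive share in the pamrevlumab arm, q the share of positives who do not enter the extension, and r the share of negatives who do not enter. The apparent share among entrants is p(1−q) / [p(1−q) + (1−p)(1−r)].

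With p = 10% (4.6 of 46 subjects):
- q = 50%, r = 5%: 0.050 / (0.050 + 0.855) = 5.5%
- q = 50%, r = 10%: 0.050 / (0.050 + 0.810) = 5.8%
- q = 25%, r = 5%: 0.075 / (0.075 + 0.855) = 8.1%
- q = 25%, r = 10%: 0.075 / (0.075 + 0.810) = 8.5%
- q = 0, r = 5%: 0.100 / (0.100 + 0.855) = 10.5%
- q = 0, r = 10%: 0.100 / (0.100 + 0.810) = 11.0%

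Over the same grid, a true 5% appears as 2.7% to 5.5%, and a true 15% as 8.5% to 16.4%. If q = r the apparent share equals p. The bias is downward only when q exceeds r.

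**The case against.** The best defence is that the SAP's phrase about the extension may describe when the analysis is run, not whose samples enter it. Appendix 3 supports this reading: its statistical paragraph says extension data will be summarized descriptively together with the main study. Pooling would also be natural. Appendix 4 schedules no HAHA draw at extension entry, so treatment-emergent ADA in a former placebo subject needs a main-study sample as its starting point. If the extension SAP pools all samples, subjects who reacted or left early are represented through their main-study draws, and so is the placebo arm. Protocol 6.2.3.2.2 sets no date, ADA is not a listed endpoint, and Protocol 8.3.7 contains no ADA analysis.

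Much of this stands. A reader might infer that the deferred ADA rate will be biased low because the extension excludes those most affected by antibodies. The documents do not support that as a fact, for three reasons:
- The analysis population is not stated, and the extension SAP was not supplied.
- The direction depends on antibody-positive subjects being lost more often than negative ones. Entry is optional, so negatives are lost too.
- The exclusions reach clinical reactors and early leavers. They do not reach an antibody-positive subject, including one with neutralizing antibodies, who has no reaction and completes Week 52.

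Whether stopping infusions bars entry is itself unclear. The opening of Appendix 3 admits Week 52 completers whatever number of infusions they received, while its Study Enrollment paragraph requires completed treatment. These passages must be reconciled.

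The defence does not remove the gap in the main-study report. On either reading this SAP specifies no ADA analysis, and Section 7 is silent. The reaction and concentration summaries elsewhere in the SAP are not linked to ADA status.

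**Conclusion.** The point holds as a gap between the protocol's commitment and the main-study SAP. Following the SAP, the main-study report would list up to about 460 to 580 scheduled samples without an incidence by arm, a placebo background rate, or any reaction or concentration summary by ADA status. That conclusion rests on the text alone.

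The concern about selection is conditional. If the later analysis uses extension entrants only, it has no concurrent placebo background and omits subjects with an allergic or anaphylactic reaction to study drug and those who left the main study early. ADA incidence would then be understated if positives are lost more often than negatives. With an assumed true rate of 10% and half the positives lost, it would appear as 5.5% to 5.8%. No actual bias can be claimed from these documents.

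The primary PUL test is unaffected. The SAP should be changed because the data exist, the protocol promised the assessment, and the remedy is cheap.

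**What to change.** Rewrite SAP 6.10 so that the main-study report contains:
- In the safety analysis set, by treatment arm: number and percentage baseline-positive, treatment-emergent, persistent and neutralizing-positive, each defined in advance, with placebo as the background rate.
- Within pamrevlumab, descriptively by ADA status: pre-dose concentration at the visits where both samples are drawn (Weeks 24, 32, 40 and 48), and hypersensitivity and infusion reactions. PK sampling needs optional consent, so show the denominators.
- PUL change by ADA status only as a descriptive table or listing. At an assumed 10% rate, only four or five of about 46 treated subjects would be positive, too few for a comparison.

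Also state that any later extension analysis includes all main-study samples from all dosed subjects, including those who did not enter the extension. Record the change in Section 7.

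The cost is SAP wording and a few tables on data already collected. No new samples or visits are needed, and no confirmatory test is added.
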